15.2 Strokes

The CEC will adjudicate all suspected strokes.

15.2.1 Major Stroke

A Major Stroke is to be defined as an increase of 5 or more in NIH Stroke Scale from baseline score and a Modified Rankin Score of ≥ 3 .

Note: If NIH ≥ 4 at enrollment, any change ≥ 5 is considered a major stroke. If Rankin ≥ 3 at enrollment, and change ≥ 1 is considered a major stroke .

15.2.2 Minor Stroke

A Minor Stroke is defined as an increase in NIH Stroke Scale score of at most 4 points from baseline and a Modified Rankin score of at least 2.

Note: If NIH ≥ 4 at enrollment, any change ≤ 4 is considered a minor stroke

15.3 Cranial Nerve Injuries

The CEC will adjudicate all suspected cranial nerve injuries that occur within 30 days (+7 days) of the procedure.

16 Statistical Methods and Determination of Sample Size

16.1 Overview

The following section provides an outline of the statistical methods to be applied to the clinical data from this study. A Statistical Analysis Plan, containing the details for generating the analyses, will be finalized prior to any analyses being conducted.

16.1.1 Sample Size Calculation

The sample size for this clinical investigation is based on the rate of procedural success within 30 days of the stent implant. The observed rate of procedural success in the ROADSTER 2 Study will be compared to an *a priori* threshold of 85% derived from the ROADSTER Study. The

rationale for an 85% threshold is based on the lower bound of the 2-sided 95% exact binomial confidence intervals of the procedural success rates from the ROADSTER Lead-In Phase (91.0%, 95% CI 81.52%, 96.64%) and the ROADSTER Pivotal Phase (95.7%, 95% CI 90.97%, 98.42%). Given that the majority of sites that will participate in the ROADSTER 2 Study will not have participated in the ROADSTER IDE, the procedural success rate must consider outcomes from early enrollment. With an observed rate of procedural success >89% in the ROADSTER 2 Study, the results will be significant with a minimum of 600 patients, meaning the lower bound of the 2-sided 95% exact binomial confidence interval will exceed 85%. Deterministically, if 534 patients of the 600 total cases (89%) were classified as a procedural success within 30 days of the stent implant, the exact 95% lower binomial confidence limit would be 86.22%.

Estimates for the 3 categories of physician level of training and experience (yes/no) will be summarized. However, given the distribution of physicians by level of training and experience will not be controlled for in this clinical investigation, it is indeterminate how informative the estimates will be.

16.2 Endpoint Analyses and Hypothesis Testing

The hypothesis testing will be focused on the proportion of patients classified as a procedural success, and to examine differences among the levels of physician training and the experience of physicians.

16.2.1 Primary Endpoint

The primary endpoint for the study is the rate of procedural success through 30 days following stent implant. The derivation of the endpoint for the primary analysis of the primary endpoint will consider all patients who undergo the procedure and in the absence of a major protocol deviation, i.e., the Per Protocol population. Patients who exit the study prior to the 30 day post-procedure evaluation who meet the definition of a procedural success based on their last observation will be counted in the analysis as a procedural success. Secondary analyses of the primary endpoint will consider alternative methods of imputation; the details of these supplemental analyses will be described in the Statistical Analysis Plan.

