16.2.2 Primary Analysis of the Primary Endpoint

The dependent variable used in the primary analysis will be dichotomous and set to *Yes* if the patient is a procedural success through 30 days following stent implant and *No* if they are not a procedural success through 30 days following stent implant. Results from the analysis of the primary endpoint will be based on a 2-sided binomial test, compared to an *a priori* threshold of 85.0%. The 2-sided 95% exact binomial confidence intervals will also be presented. Patients who withdraw prior to 30 days, but at the time of withdraw were tracking to meet the definition of a procedural success, will be counted in the analysis as a procedural success.

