16.4 Populations for Analysis

The Per-Protocol population is defined as patients who sign an informed consent, undergo the study procedure, independent of the success of the procedure, and with the absence of major protocol deviations. Patients who sign an informed consent, however fail to undergo the study procedure, will not be included in the Per-Protocol population. A maximum of 30 patients treated per protocol per physician can contribute to the 600 patient minimum. A physician may enroll more than 30 patients.

The primary endpoint and all secondary endpoints will be analyzed based on the Per-protocol population. All available data on the Per-Protocol patients who enrolled in the study will be included. Any subject not meeting the Inclusion/Exclusion criteria will be tabulated but not included in the primary endpoint analysis.

17 Data Collection

Data will be entered into a validated electronic data management system. Data fields in the selected electronic data management system used will be aligned such that it overlaps with the appropriate data fields for the post-approval study as derived from the ROADSTER IDE.

18 Sponsor Responsibilities

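### Do sections 16.2.1 and 16.2.2 give conflicting rules for patients who leave before the 30-day evaluation?

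*Combined protocol and SAP*

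**What the plan says.** Section 16.2.1 sets out how the endpoint is derived for the primary analysis. It takes all treated patients without a major protocol deviation and counts as successes "Patients who exit the study prior to the 30 day post-procedure evaluation who meet the definition of a procedural success", judged on the last observation. It adds that "Secondary analyses of the primary endpoint will consider alternative methods of imputation", with the details left to the SAP.

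Section 16.2.2 defines the dependent variable. A patient is coded Yes if a procedural success through 30 days and No "if they are not a procedural success through 30 days following stent implant". The section ends with its own sentence on early leavers: "Patients who withdraw prior to 30 days, but at the time of withdraw were tracking to meet the definition of a procedural success" are also counted as successes.

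Section 16.4 defines the Per-Protocol population as consenting patients who "undergo the study procedure, independent of the success of the procedure, and with the absence of major protocol deviations". It sets no follow-up requirement and states that "All available data on the Per-Protocol patients who enrolled in the study will be included". Section 16.1 says that a SAP with the analysis details will be final before any analysis is run.

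**The concern.** The primary analysis is a pass/fail comparison with 85% in an open-label, single-arm study, so the rule that turns an unobserved outcome into a success should have one reading. Here it has two wordings. One speaks of leaving the study, the other of withdrawing. One stops the clock at the 30-day evaluation, the other at day 30. One asks whether the definition is met at the last observation, the other whether the patient was on course to meet it.

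Because section 16.4 keeps treated patients in the denominator whatever their follow-up, each early leaver needs a value. A programmer who worked from section 16.2.2 alone might score a patient lost to follow-up as No or as missing, while one who worked from section 16.2.1 would score the same patient as Yes. Near the decision boundary a handful of such patients could settle the result.

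**Working it through.** **Step 1. The two sentences side by side**

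| Element | 16.2.1 | 16.2.2 |
|---|---|---|
| Event | leaves the study | withdraws |
| Time | before the 30-day evaluation | before day 30 |
| Status | definition met when last seen | on course to meet it at withdrawal |
| Consequence | success | success |

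The first three rows differ. The last does not. Neither sentence says that only the patients it names qualify, and neither assigns a failure.

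**Step 2. Patients who might fall between them**

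- *Patient A* is lost to follow-up after discharge and met the definition when last seen. Section 16.2.1 makes this patient a success. Section 16.2.2 does not mention loss to follow-up, but its No category is for patients who are not successes; it does not address patients whose status is unknown. Taken together: success.
- *Patient B* withdraws on day 33, before a late evaluation. Section 16.2.1 makes this patient a success if the definition was met at the last observation. The time limit in section 16.2.2 does not reach day 33, but the patient was still in the study on day 30, which is the endpoint's horizon. Taken together: success. The example also needs a visit window. The only one in the available text is in section 15.3, "The CEC will adjudicate all suspected cranial nerve injuries that occur within 30 days (+7 days) of the procedure", and it concerns adjudication of nerve injuries.
- *Patient C* withdraws early and is on course, but the last observation does not yet meet the definition. Section 16.2.2 makes this patient a success; the sentence in section 16.2.1 does not reach the patient. Whether such a patient can exist depends on the definition of procedural success, which is not in the available text. Success is assessed through 30 days, so nobody last seen earlier can have met it in full. Section 16.2.1 therefore has an effect only if its test means met so far, which is close to being on course. On that reading Patient C disappears.

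**Step 3. What the wording could be worth**

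Inputs: threshold 85%, two-sided 95% exact interval and n = 600, from sections 16.1.1 and 16.2.2. The exact lower limit for x successes in n is the 0.025 quantile of a Beta(x, n − x + 1) distribution.

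The plan's own example is "if 534 patients of the 600 total cases (89%) were classified as a procedural success within 30 days of the stent implant". Beta(534, 67) gives 86.22%, as section 16.1.1 states.

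Decision boundary:

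- 528/600: Beta(528, 73) gives 85.13%, above 85%.
- 527/600: Beta(527, 74) gives 84.95%, below 85%.

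Number of disputed patients that would reverse the result if all were scored as failures:

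- from 534/600 (89%): 534 − 527 = 7, or 7/600 = 1.2%;
- from 546/600 (91.0%, the earlier lead-in rate): 546 − 527 = 19, or 3.2%;
- from 574/600 (95.7%, the earlier pivotal rate): 574 − 527 = 47, or 7.8%.

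If they were removed from numerator and denominator instead, 534/600 would tip only at 50 patients: 484/550, Beta(484, 67), lower limit 84.99%. Removal would also go against section 16.4.

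These are break points, not forecasts. The documents give no exit rate. The first set also measures the distance between section 16.2.1 and a failure imputation, and Step 1 shows that no section calls for one.

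**The case for a change.** The strongest argument for a change is that nothing in the available text says the two sentences are equivalent or which of them governs. The deferral to the SAP in section 16.2.1 covers the secondary analyses only, not the primary rule. Reading the two together is an inference, and it leaves the on-course test of section 16.2.2 undefined. Both wordings impute in the favourable direction, so any looseness favours a pass. Harmonising them would cost one sentence.

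Part of this stands. The wordings do differ on three points, the on-course test has no definition in the available text, and it could be looser than the test in section 16.2.1, so it is not established which sentence reaches more patients. One wording would be tidier.

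What does not stand is the step from different words to different results. Section 16.2.1 announces that it derives the endpoint for the primary analysis. Section 16.2.2 then codes that endpoint and restates the rule more loosely. An analyst who has both subsections in front of them has an explicit instruction for a patient lost to follow-up, and no instruction that overrides it. Whether it is wise to carry success forward at all is a separate question: both sections share that choice, and the promised alternative imputations address it.

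**Conclusion.** The concern does not call for a change. The two sections express one favourable rule in two forms of words. Both lead to success, and following the plan as written has not been shown to give a wrong or contradictory classification. The break point of seven patients from 534/600 would matter only under failure scoring that neither section prescribes; at the earlier pivotal rate it would take 47.

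This rests on reading sections 16.2.1 and 16.2.2 together, and on taking the No category to mean observed non-success rather than unknown status. It also allows that the sections between the summary and section 15, and the separate SAP, were not available and may define leaving, withdrawing, the visit window and procedural success. If leaving means withdrawing and the visit has no window, the event and time differences vanish as well. The remaining ambiguity is a detail that the SAP author can settle before analysis, as section 16.1 provides, without altering the primary rule.

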16.2.2 Primary Analysis of the Primary Endpoint

The dependent variable used in the primary analysis will be dichotomous and set to *Yes* if the patient is a procedural success through 30 days following stent implant and *No* if they are not a procedural success through 30 days following stent implant. Results from the analysis of the primary endpoint will be based on a 2-sided binomial test, compared to an *a priori* threshold of 85.0%. The 2-sided 95% exact binomial confidence intervals will also be presented. Patients who withdraw prior to 30 days, but at the time of withdraw were tracking to meet the definition of a procedural success, will be counted in the analysis as a procedural success.

16.2.3 Secondary Endpoint

The analyses to be conducted on the secondary endpoints are intended to provide additional supportive evidence of the efficacy and safety of the device. There are 10 secondary endpoints that will be assessed at 30 days post-procedure; each of the secondary endpoints is a dichotomous variable:

- Acute device success
- Technical success
- Rate of cranial nerve injury

- Rate of cardiac death
- Rate of neurological death
- Rate of hierarchical ipsilateral stroke, death and MI
- Rate of hierarchical ipsilateral stroke, death and MI by symptom status
- Acute device, technical and procedural success by physician experience
- Acute device, technical and procedural success by physician training level
- Acute device, technical and procedural success by enrollment quartile

16.3 Statistical Methods

The pre-procedure observations will serve as the *baseline* values for calculating post procedure changes from baseline. Tabulations of summary statistics, graphical presentations, and statistical analyses will be performed using SAS software version 9.2 or higher. The statistical analyses will be based on data pooled across *Sites* in aggregate; a secondary tabulation will be prepared separately for the US and Non-US sites. Continuous demographic parameters, such as the age of the patient at the time of enrollment, will be summarized for the Per-Protocol population using descriptive statistics (N, mean, median, standard deviation, minimum and maximum value, and 95% 2-sided confidence limits). Continuous demographic parameters will be compared among the 3 levels of physician training and experience using a 1-factor (physician training [1, 2 or 3]; physician experience [participation in ROADSTER 1 or no participation in ROADSTER 1]) analysis of variance model. Contrast statements will be used to evaluate the individual pair wise comparisons (Level 1 vs. Level 2, Level 1 vs. Level 3, and Level 2 vs. Level 3; participation in ROADSTER 1 vs no participation in ROADSTER 1). Categorical demographic parameters, such as gender, will be summarized as a proportion of the Per-Protocol population using Clopper-Pearson 95% 2-sided confidence limits. The categorical demographic parameters will be compared using a Mantel-Haenszel test stratified on physician level of training (1, 2, or 3) and separately by physician experience (participation in ROADSTER 1 vs no participation in ROADSTER 1). Additionally, a generalized linear model (PROC GENMOD) will be used to evaluate the main effect of physician level of experience, specifying the distribution as either binomial or multinomial. Clinical and high risk factors will also be summarized as a proportion of the Per-Protocol population with Clopper-Pearson 95% 2-sided confidence limits. In addition to the overall summary of the individual factors, separate summaries will be generated by physician experience and level of training. Comparisons will be made among the 3 levels of physician training and physician experience (participation in ROADSTER 1 vs no participation in ROADSTER 1), depending on the type and distribution of the parameter.

Data obtained during the neurological examination, including data from the NIH Stroke Scale, Modified Rankin Scale and Cranial Nerve Palsy Assessment will be summarized at each time point using descriptive statistics. Separate summaries will be generated by level of physician training and experience and compared using a 1-factor (physician level of training [1, 2 or 3]) and a 1-factor (experience: participation in ROADSTER 1 vs. no participation in ROADSTER 1) analysis of variance model. Contrast statements will be used to evaluate the individual pair wise comparisons (Level 1 vs. Level 2, Level 1 vs. Level 3, and Level 2 vs. Level 3).

Specific algorithms for imputing missing or partially missing dates will be discussed in the SAP. Derived data will be identified in the individual patient data listings. Imputed data for dates will not

be incorporated into the case report form datasets. Imputed data for dates will be used in the preparation of the derived datasets.

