POST-APPROVAL STUDY of TRANSCAROTID ARTERY
REVASCULARIZATION in PATIENTS with SIGNIFICANT CAROTID
ARTERY DISEASE.

The ROADSTER 2 Study

Clinical Protocol	SRM-2015-02
Version	E
Version Date	February 10, 2017

NCT02536378

Sponsored by:

Silk Road Medical, Inc.
[name]
[name]
United States of America
[contact]
[contact]

1 Protocol Summary

Title	POST-APPROVAL STUDY of TRANSCAROTID ARTERY REVASCULARIZATION in PATIENTS with SIGNIFICANT CAROTID ARTERY DISEASE. (The ROADSTER 2 Study)
Objective	The ROADSTER 2 Study is intended to evaluate real world usage of the ENROUTE Transcarotid Stent when used with the ENROUTE Transcarotid Neuroprotection System by physicians of varying levels of training and previous experience with the transcarotid technique.
Study Design	The ROADSTER 2 Study is an open label, single arm, multi-center post-approval Study for the treatment of patients at high risk for adverse events from carotid endarterectomy who require carotid revascularization and who are eligible for treatment with a combination of the ENROUTE Transcarotid Stent System and the ENROUTE Transcarotid NPS.
Enrollment	A minimum of 600 patients treated per protocol. Enrollment will be an entirely new cohort of patients. Additional follow-up on subjects from the ROADSTER IDE will not be included. A maximum of 30 patients per physician will be included in the first 600 patients. A physician may enroll more than 30 patients.
Investigation Site Locations	A minimum of 30 and up to a maximum of 100 sites in the United States. A maximum of 5 sites in the European Union. No more than 30% of the sites will be sites that previously enrolled in the ROADSTER study.
Primary Endpoint	The rate of procedural success through 30 days following stent implant.
Secondary Endpoints	The following secondary endpoints will be assessed 0 to 30 days: 
 ▪ Acute device success ▪ Technical success ▪ Rate of cranial nerve injury ▪ Rate of cardiac death ▪ Rate of neurological death ▪ Rate of hierarchical ipsilateral stroke, death and MI ▪ Rate of hierarchical ipsilateral stroke, death and MI by symptom status ▪ Acute device, technical and procedural success by physician experience ▪ Acute device, technical and procedural success by physician training level ▪ Acute device, technical and procedural success by enrollment quartile

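### Section 16.3: PROC GENMOD with a multinomial distribution fits ordered-category models, so for any nominal demographic with three or more categories the p-value would depend on an arbitrary category order

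*Combined protocol and SAP*

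**What the plan says.** Protocol section 16.3 fixes the software: "statistical analyses will be performed using SAS software version 9.2 or higher". For categorical demographics it plans three things.

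- A summary: "Categorical demographic parameters, such as gender, will be summarized as a proportion of the Per-Protocol population", with exact confidence limits.
- A comparison: "The categorical demographic parameters will be compared using a Mantel-Haenszel test stratified on physician level of training (1, 2, or 3"). The same test is planned a second time with ROADSTER 1 participation as the physician factor. The version of the Mantel-Haenszel statistic is not given.
- A model on top of that test: "a generalized linear model (PROC GENMOD) will be used to evaluate the main effect of physician level of experience, specifying the distribution as either binomial". The sentence then offers multinomial as the alternative distribution.

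The model sentence gives no link function, no category order, no split between nominal and ordered variables, and no generalized-logit alternative. Gender is the only categorical demographic named. Section 16.1 calls the section an outline and leaves details to a Statistical Analysis Plan, but nothing in the supplied text takes this point further.

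**The concern.** Binomial already covers two-category variables, so allowing for multinomial makes sense only if variables with three or more categories are expected. For those, GENMOD fits a cumulative-link model, which is a model for ordered categories. A two-level factor such as ROADSTER 1 participation then gets one coefficient, which measures a shift along the assumed order.

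A nominal variable has no such order, so one must be imposed when the model is fitted. A difference between physician groups that is not a shift along that order may go undetected, and reordering the categories can change the p-value.

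At stake is the description of case mix. Section 16.1.1 says that the distribution of physicians by training and experience is not controlled, and success by physician experience is a secondary endpoint. A reader will look at these comparisons to see whether the physician groups treated similar patients.

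**Working it through.** **The plan's own figure.** The plan gives no figure on this point. Its one sample-size result, in 16.1.1, is an exact lower limit of 86.22% for 534/600. It reproduces (beta quantile at 0.025 with parameters 534 and 67 = 86.219%) and plays no part in what follows.

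**Inputs**

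- Total of 600 patients: "A minimum of 600 patients treated per protocol" (Protocol Summary, Enrollment).
- Experienced share of 30%: an assumption, giving 0.30 × 600 = 180 against 420. The Protocol Summary caps former ROADSTER sites at 30% of sites; it does not cap patients.
- Three nominal categories A, B, C with the counts below: assumed.
- Two-sided alpha 0.05 for the rejection rates: assumed, since 16.3 states none for this test.
- GENMOD's multinomial option offers only cumulative links (logit, probit, complementary log-log): general software knowledge.

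**Step 1: order-free test.**

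| | A | B | C | Total |
|---|---|---|---|---|
| Experienced | 126 | 36 | 18 | 180 |
| Other | 294 | 42 | 84 | 420 |

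Expected counts are 126, 23.4, 30.6 and 294, 54.6, 71.4. A contributes nothing. Every B and C cell differs from expectation by 12.6, and 12.6² = 158.76. Chi-square = 158.76/23.4 + 158.76/30.6 + 158.76/54.6 + 158.76/71.4 = 6.78 + 5.19 + 2.91 + 2.22 = 17.10 on 2 df, p = 0.0002.

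**Step 2: cumulative logit on the same table.** The model is logit P(Y ≤ k) = a_k + b × group, with one b for all cut-points, tested by likelihood ratio on 1 df.

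| Order | Odds ratio at cut 1 (other vs experienced) | Odds ratio at cut 2 | LR chi-square | p |
|---|---|---|---|---|
| A-B-C | 1.00 (70% vs 70%) | 0.44 (80% vs 90%) | 0.51 | 0.476 |
| A-C-B | 1.00 (70% vs 70%) | 2.25 (90% vs 80%) | 0.54 | 0.462 |
| B-A-C | 0.44 (10% vs 20%) | 0.44 (80% vs 90%) | 17.18 | 0.00003 |

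The odds ratios come straight from the cumulative percentages, for example (0.80/0.20)/(0.90/0.10) = 4/9 = 0.44. With A first, the cut between A and the rest shows no difference and pulls the single coefficient towards zero. With A in the middle, both cuts show the same odds ratio and the model fits exactly. Reversing an order leaves the logit p-value unchanged, so three categories give three distinct results.

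**Step 3: how often imbalance is detected** (simulation, 180 against 420, assumed shares).

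| Shares, experienced vs other | Pearson | Cumulative logit (A-B-C / A-C-B / B-A-C) |
|---|---|---|
| 80/13/7 vs 80/7/13 | 77% | 6% / 7% / 85% |
| 40/30/30 vs 47.5/15/37.5 | 97% | 4% / 85% / 91% |
| 90/6/4 vs 80/12/8 | 80% | 90% / 90% / 6% |

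In the third row the cumulative logit beats Pearson in two orders and fails in one.

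**Step 4: no true imbalance.** With the same shares in both groups (45/20/35), the cumulative logit rejects in 4.5% to 5.3% of simulations across the orders, and Pearson in 4.3%. False positives are not inflated.

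**The case against.** The strongest case on the other side concerns reach.

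- **No affected variable is named.** Gender is binary, and unnamed multi-category variables could be ordinal, for which a cumulative link is appropriate. This stands: the point is conditional on a nominal demographic with three or more categories being tested.
- **The premise about the software is not in the documents.** True, and it is stated here as an assumption. It describes a procedure that the plan itself names.
- **Section 16.1 defers detail to the SAP.** Partly stands. Link and ordering are normal SAP content, but 16.3 already fixes the procedure and the distribution, and an analyst who follows it literally on a nominal variable gets the ordinal model. The closing sentence of that paragraph of 16.3 ties the choice of comparison to the type of parameter, but it follows the clinical and high-risk factors, not the demographics.
- **GENMOD is an addition to a Mantel-Haenszel test.** True, but that test is not a clear safeguard. As worded it is stratified on the physician factor, and so does not itself compare physician groups. Its version is not stated, and a correlation version would depend on order too.
- **The main illustration is unfavourable by construction.** True. It holds the largest category equal and lets the two smaller ones move in opposite directions; the third row of the simulation table shows a different picture.

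A reader might infer that the study's comparison of success by physician experience is unsound, or that case-mix imbalance will go unseen. The documents support neither. The secondary endpoints are dichotomous, no rule uses a demographic p-value to adjust or gate anything, and proportions summarized by physician group would still show an imbalance whatever the p-value says.

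**Conclusion.** The point holds as a minor one. For a nominal demographic with three or more categories, the planned model gives a p-value that depends on an arbitrary ordering, and some imbalances can be missed. In the worked table p runs from 0.00003 to 0.476 on identical data, against an order-free p = 0.0002. In the simulated cases detection ranges from 4% to 91% by order.

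This rests on the assumed counts, the assumed 180/420 split, the software premise, and such a variable being analysed. It would go too far to say that the cumulative logit is generally weaker than Pearson's test, or that it produces false signals of imbalance. Binary and truly ordinal variables, the dichotomous secondary endpoints and the primary test against 85% are untouched.

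**What to change.** In 16.3, or in the SAP sentence that implements it:

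- Keep PROC GENMOD for binary parameters (binomial) and for ordinal parameters (multinomial), with the category order stated for each ordinal one.
- For nominal parameters with three or more categories, use a generalized-logit model (PROC LOGISTIC, LINK=GLOGIT), or a Pearson test, or a Fisher-Freeman-Halton test where cells are small, in each case comparing the physician groups directly.

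No new data are needed. The cost is a different procedure call and more degrees of freedom for nominal variables (2 instead of 1 with three categories and two physician groups). That loses some power when the difference happens to be a shift along the order that would have been used. Ordinal and binary variables lose nothing, since their analysis does not change.

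### Section 16.3 compares neurological data by physician training and ROADSTER 1 participation with 1-factor ANOVAs that have no physician or site term; any positive within-physician correlation makes their standard errors too small (supportive analyses only)

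*Combined protocol and SAP*

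**What the plan says.** Section 16.3 covers the stroke-scale, Rankin and cranial nerve data at each time point and states: "Separate summaries will be generated by level of physician training and experience and compared using a 1-factor" analysis of variance on three training levels, and a second such model on ROADSTER 1 participation. For training it adds: "Contrast statements will be used to evaluate the individual pair wise comparisons". The demographics paragraph of the same section describes the second factor as "physician experience [participation in ROADSTER 1 or no participation in ROADSTER 1" (the bracket closes in the text). It also sets the general approach: "The statistical analyses will be based on data pooled across" sites.

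The supplied text contains no physician effect, site effect, mixed model, GEE or robust variance.

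Section 16.4 says: "A maximum of 30 patients treated per protocol per physician can contribute to the 600 patient minimum". It then lets a physician go beyond 30, and adds: "All available data on the Per-Protocol patients who enrolled in the study will be included". So the limit governs who counts toward the 600, not how many patients of one physician enter these analyses.

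**The concern.** Training level and ROADSTER 1 participation are properties of the physician, or of the site, since the Protocol Summary counts earlier participation by site. All patients of one physician therefore share the same factor value. A 1-factor model on patient data treats those patients as independent. If they resemble each other at all, the model overstates the information about the factor, and the standard errors of the group differences and contrasts are too small.

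The study objective concerns use of the device "by physicians of varying levels of training and previous experience with the transcarotid technique", so readers will look at these comparisons. The results of a few busy physicians could be read as a training or experience effect. What is at stake is a misleading p-value in a supportive analysis.

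**Working it through.** **The plan's own figure.** The documents give no figure for these ANOVAs. The one figure that can be checked is the sample-size statement in 16.1.1: for 534 of 600, the exact lower limit is the 2.5% quantile of Beta(534, 67) = 86.22%, as stated. It concerns the primary endpoint and is not affected by this point.

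**Inputs from the documents.** At least 600 per-protocol patients and 30 to 100 US sites (Protocol Summary); three training levels and two participation groups (16.3).

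**Assumptions, not in the documents.** ICC 0.01 to 0.05; nominal 5% level; equal enrolment; equal thirds by training level; normal outcome; one physician per site; training level fixed during the study (its definition is not in the supplied text). One physician per site gives 600/100 = 6 to 600/30 = 20 patients per physician. Several physicians per site would mean fewer.

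**Step 1, design effect.** For a factor constant within physician and m patients each, DE = 1 + (m − 1) × ICC. The true standard error is √DE times the stated one.
- m = 6: DE 1.05 to 1.25, so 1.025 to 1.118.
- m = 10: DE 1.09 to 1.45, so 1.044 to 1.204.
- m = 20: DE 1.19 to 1.95, so 1.091 to 1.396.

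**Step 2, actual rejection rate, three levels.** In large samples the test compares DE × χ²(2) with 5.991, so the rate is exp(−5.991 / (2 × DE)), which equals 0.05^(1/DE). For m = 6 and ICC 0.05 this is 0.05^(1/1.25) = 9.1%. Simulation with finite degrees of freedom agrees to about 0.1 percentage point.

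| Patients per physician | DE | Formula | Simulation |
|---|---|---|---|
| 2 to 3 | 1.01 to 1.10 | 5.1 to 6.6% | 5.1 to 6.5% |
| 6 | 1.05 to 1.25 | 5.8 to 9.1% | 5.8 to 9.2% |
| 10 | 1.09 to 1.45 | 6.4 to 12.7% | 6.4 to 12.7% |
| 20 | 1.19 to 1.95 | 8.1 to 21.5% | 8.0 to 21.6% |

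At ICC 0 the rate is about 5% throughout.

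**Step 3, two levels or one contrast.** The rate is 2 × (1 − Φ(1.96/√DE)): 5.6 to 8.0% at m = 6 and 7.2 to 16.1% at m = 20.

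**Step 4, unequal enrolment.** With 10 physicians treating 30 patients and 50 treating 6 (10 × 30 + 50 × 6 = 600), the simulated three-level rate for a normal outcome is 7.3 to 19.3%.

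**Step 5, non-normal scores.** A mostly zero score was simulated: 8% non-zero, size 1 + Poisson(1.5), and ICC 0.01 to 0.05 on the event. The ICC of the score itself is lower by the factor 0.0736 × 6.25 / 0.58 = 0.79, so about 0.008 to 0.040. Rates were 5.4 to 8.1% at m = 6 and 7.1 to 17.6% at m = 20. A normal outcome at those same ICCs gives 5.6 to 8.2% and 7.4 to 18.2%. The lower rates thus mostly reflect the lower ICC rather than the skewness.

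**Step 6, shared sites.** With 30 sites of 2 physicians and 10 patients each, ICC 0.025 for site and 0.025 for physician, and a factor common to the site, the patient-level ANOVA rejects 17.2%, ANOVA on physician means 7.9% and ANOVA on site means 5.0%. The unit of analysis must be the one at which the factor varies.

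**The case against.** **The size is conditional.** This stands. Nothing in the documents shows that the ICC of these scores is above 0, and 16.1.1 says the physician mix is uncontrolled, so equal thirds is only a convenience. The 20-patient case needs the minimum number of US sites, no EU sites and one physician per site. At ICC 0.01 with 2 to 6 patients per physician the inflation is negligible. The direction for any positive ICC does not depend on these inputs.

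**Detail is left to a later SAP (16.1).** That is a place to correct the model. But 16.3 already states the model, and a SAP that follows it inherits the fault.

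**The plan already warns that these estimates may be uninformative (16.1.1).** That caveat concerns the uncontrolled distribution of physicians, not correlation between their patients. It does not make the p-values valid.

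**Stronger readings that the documents do not support.** A reader might infer from 16.2, where hypothesis testing is also meant "to examine differences among the levels of physician training and the experience of physicians", that the main hypothesis tests are compromised. That sentence most naturally refers to differences in procedural success. Section 16.2.3 lists success by training and experience but names no test for it, and the generalized linear model in 16.3 appears among the categorical demographics. The same fault would arise for success only if a patient-level test were chosen. A reader might also infer that the primary result is wrong. The primary analysis in 16.2.2 is a separate binomial test against 85%, with no training or experience factor. Finally, 16.3 does not forbid a physician term; it simply states none.

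**Conclusion.** The point holds, as a minor one. The ANOVAs of neurological data stated in 16.3 have the wrong error term for factors that vary only between physicians or sites, and they are anti-conservative whenever within-physician correlation is positive. Under the assumptions listed in the working, the false-positive rate ranges from barely above nominal (2 to 3 patients per physician) to about four times nominal (20 per physician, ICC 0.05). The upper end is a corner of the assumed range, not a forecast. The ANOVA of continuous demographics in 16.3 has the same structure but matters less. No alpha or decision rule is attached to any of these comparisons, so no study conclusion turns on them.

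**What to change.** In 16.3, or in the SAP promised in 16.1, keep the two factors and the contrasts and replace the 1-factor ANOVA of neurological data by a linear mixed model:
- a random physician intercept, plus a random site intercept where physicians share a site;
- denominator degrees of freedom equal to the number of units at which the factor varies (physicians, or sites if ROADSTER 1 participation is coded by site) minus the number of groups.

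ANOVA on the means of those same units is a simple check. Unweighted means average over physicians or sites, not over patients, and the text should say so.

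**Does it work?** In simulations without shared sites (equal and unequal enrolment, ICC 0 to 0.05), the random-intercept test rejected 2.5 to 6.0%, the low values near ICC 0. ANOVA on physician means rejected 4.2 to 5.5%.

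**Cost.** No new data are needed, because the 30-patient limit already requires physician identity. Standard errors widen by about 2.5 to 12% at 6 patients per physician and by up to 40% at 20. A three-level effect with 80% power under independence would have 77 to 69% at 6 per physician and 67 to 46% at 20 (ICC 0.01 to 0.05; noncentral F with noncentrality 9.683/DE and physicians minus 3 degrees of freedom). At ICC 0 the power would be 78.9% and 75.3%. When the ICC is positive, most of this loss is precision that the patient-level model wrongly claimed. The primary exact binomial analysis stays as it is.
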